- 8) Therapy with any of the following: IL-2, interferon, or other non-study immunotherapy regimens; cytotoxic chemotherapy; immunosuppressive agents; target molecular inhibitors (BRAF, MEK, KIT); or chronic use of systemic corticosteroids (used for the management of non-cancer related illnesses), either concomitantly or during the last 3 weeks prior to the beginning of the treatment.
- 9) Any experimental therapy administered in the past 30 days prior to the beginning of the treatment.
- 10) Any non-oncology vaccine therapy used for the prevention of infectious diseases (for up to 4 weeks prior to or after any dose of blinded study drug)
- 11) Women of childbearing potential (WOCBP), as defined above in “Inclusion criteria”, who:
 - a. are unwilling or unable to use an acceptable method of contraception to avoid pregnancy for their entire study period and for at least 26 weeks after cessation of study drug, or
 - b. have a positive pregnancy test at baseline, or
 - c. are pregnant or breastfeeding.
- 12) Prisoners or subjects who are compulsorily detained (involuntarily incarcerated) for treatment of either a psychiatric or physical (eg, infectious) illness.
- 13) Any other general, medical or psychological conditions which in the opinion of the investigator will make the administration of ipilimumab hazardous, or that would preclude appropriate informed consent or compliance with the protocol, or obscure the interpretation of eventual AEs.

4.3 **Data Safety Monitoring Plan**

A Data Safety Monitoring Committee (DSMC) will be designated prior to the initiation of the study, and chaired by the coordinating principal investigator. The DSMC will meet approximately every 4 months to ensure that subject safety is carefully monitored. The DSMC might also be consulted on an *ad-hoc* basis should a safety signal emerge, and may also convene an *ad-hoc* meeting on its own initiative. Following the review, the DSMC will recommend continuation, modification, or discontinuation of the study based on observed toxicities.

The DSMC will have access to reports of study data including analyses addressing population characteristics, dosing, safety, and efficacy updated as available prior to each of its meetings.

5. **STUDY THERAPY**

5.1. **Ipilimumab**

5.1.1. **Dose Calculations**

Each patient will receive ipilimumab 3 mg/Kg every 3 weeks, for a total of 4 administration. Infusions should be given over 90 minutes (not bolus or IV push).

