6.4.2. Efficacy Evaluation

The primary endpoint will be 1-year survival. Secondary endpoints require the assessment of disease progression or response to therapy.

Secondary response-based endpoints (PFS, BORR, DCR, and duration of response) will be captured using two distinct but related criteria:

- Modified WHO (mWHO) criteria.
- Immune-related Response Criteria (irRC)

The mWHO criteria will be used to define response-based secondary endpoints. The irRC will be used to a) define exploratory endpoints and to b) define confirmed disease progression for the purpose of discontinuing ipilimumab treatment in order to permit physicians to continue treating with ipilimumab in spite of the appearance of small new lesions and/or transient increases in tumor burden that may signal anti-cancer inflammation. The irRC criteria will be used for exploratory analyses. Tumor response will be based on investigator assessment.

Tumor assessment of the disease will be performed with CT/MRI of brain, chest, abdomen and pelvis at baseline, at weeks 12 and 16-18 and then, every 8-10 weeks. The same method of assessment (CT or MRI) should be used throughout the patient's time on study for consistent evaluation of response.

6.4.2.a Radiological Assessment of Tumor Lesions

CT/MRI imaging of the brain, chest and abdomen-pelvis is required at Screening (ie, Baseline) and at each tumor assessment visit, regardless of the location of known metastases. In addition, CT/MRI scans must be obtained of anatomic regions not covered by the chest and abdomen scans, in subjects where there is clinical suspicion for deep soft tissue metastases (eg, lesions in the thigh). Such additional CT/MRIs will be required at Screening only when deep soft tissue disease is suspected during Screening and must be consistently repeated at all tumor assessment visits if a deep soft tissue lesion is identified during Screening. In cases without suspicion for deep soft tissue disease, no such CT/MRIs are required.

Obviously, brain scans are required at Screening and at each disease evaluation visit. MRIs are preferred, contrast-enhanced CTs are a second choice.

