- Progressive Disease (PD): Appearance of any new lesion(s) and/or unequivocal progression of non-index lesion(s) (eg, an increase in pleural effusions, or other fluid collections defined as an approximate doubling of the volume which was present at baseline or nadir, unless there is radiographic evidence of a benign cause for the fluid collection or the effusion is cytologically negative for malignant cells).

6.4.2.f Response per Time Point

OR is determined as the combination of assessments of index and non-index lesions using the following criteria presented in Table 13

Table 13: Overall Response per mWHO

Index Lesions	Non-index Lesions	New Lesions	Overall Response
CR	CR	No	CR
CR	IR/SD	No	PR
PR	CR or IR/SD	No	PR
SD	CR or IR/SD	No	SD
PD	Any	Yes or No	PD
Any	PD	Yes or No	PD
Any	Any	Yes	PD

6.4.2.g Best Overall Response (BOR)per Subject (Including all TimePoints)

BOR is the best confirmed response designation over the study as a whole, recorded between the date of first dose until the last tumor assessment prior to subsequent therapy (except for local palliative radiotherapy for painful bone lesions) for the individual subject in the study. The assessment of response at 12 weeks has particular emphasis due to the mechanism of action of ipilimumab inducing immune responses as basis for clinical responses. For the assessment of BOR, all available assessments per subject are considered. CR or PR determinations included in the BOR assessment must be confirmed by a second (confirmatory) evaluation meeting the criteria for response and performed no less than 4 weeks after the criteria for response are first met.

Consistent with the definition of BOR in this study, the date of disease progression is defined for each subject based on post-Week 12 time points, in cases where a subject had an OR of CR, PR or SD at Week 12. BOR assessment of SD requires an OR of SD (or unconfirmed PR or CR) at Week 12, in the absence of BOR of CR, PR or PD.

The following criteria (Table 14) summarize the combination of assessments of OR at different time points throughout the study to establish BOR for the individual subject with emphasis on the 12 week time point due to the mechanism of action of ipilimumab:

Table 14. Assessment of Best Overall Response

Overall Response At Time Points Before Week 12	Overall Response At Week 12	Overall Response At Time Points After Week 12	Best Overall Response For All Time Points
CR* or PR*	Any	Any	CR or PR (at time point before Week 12)

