8.3.3. Nonserious Adverse Events

The collection of nonserious AE information should begin at initiation of investigational product. In general, the collection period will last for 30 days after the last treatment administration. The exceptions are the immune-related AEs that occur within 90 days of discontinuation of dosing of the investigational product, which should also be collected.

If an ongoing nonserious AE worsens in its intensity, or if its relationship to the investigational product changes, a new nonserious AE entry for the event should be completed.

Nonserious AEs should be followed to resolution or stabilization, or reported as SAEs if they become serious. Follow-up is also required for nonserious AEs that cause interruption or discontinuation of investigational product, or those that are present at the end of study participation. Subjects with nonserious AEs at study completion should receive post-treatment follow-up as appropriate.

All identified nonserious AEs must be recorded and described in the medical record.

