9.4.3 Safety Analyses

Descriptive statistics of safety will be presented for all treated subjects using the National Cancer Institute (NCI) Common Terminology Criteria for Adverse Events (CTCAE) version 4.0. All on-study AEs, drug-related AEs, immune-related AEs, SAEs, and drug-related SAEs will be tabulated using worst grade

per NCI CTCAE v4.0 criteria by system organ class and by preferred term. The listings by subject will be produced for all deaths, all SAEs, and all AEs leading to discontinuation of study drug. On-study laboratory parameters, including hematology, serum chemistry, liver function, and renal function will be summarized using worst grade per NCI CTCAE v4.0 criteria. The reporting period for safety data will be from the first dose of study medication to 90 days (> 5 half lives) after the last dose is received.

Immune-related Adverse Events (irAEs)

Immune-related adverse events (irAEs) are AEs of unknown etiology, which are consistent with an immune phenomenon and identified by the investigator as study treatment related. The irAEs will be defined using a predefined list of MedDRA highlevel group terms, high-level terms and preferred terms; changes may be made to this list with each new version of MedDRA. Six (6) subcategories of irAEs will be reported: GI, liver, skin, endocrine, neurological, and other. Immune-related AE summaries will also be produced on diarrhea as a separate grouped term. Analysis of irAEs will be based on all treated subjects who received at least one dose of study therapy, and the reporting period will be from the first dose of after the last dose is received.

Immune-mediated Adverse Reactions (imARs)

This study will also describe immune-mediated adverse reactions (imARs) using the same adjudication algorithm and predefined list of AEs of special interest (enterocolitis, hepatitis, dermatitis, endocrinopathies, neuropathies, and other) used for the USPI. Specifically, the determination of imAR will take into account available clinical evidence through ruling out non-inflammatory etiologies such as infection or tumor progression, and consideration of evidence of inflammation such as tumor biopsies or responsiveness to steroids, but not the causality assessment of the investigator. imARs are likely to be

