1.6. TOXICITIES (Treatment-related AEs)

As specified in the protocol for this analysis, was used the population of treated patients, n = XX.

Table 41. Toxicities

		N (% ¹ ; 95% CI)
Patients with at least one toxicity, any grade	No	
	Yes	
	Total	
Patients with at least one gradetoxicity≥3	No	
	Yes	
	Total	
Patients with grade 3 toxicities	No	
	Yes	
	Total	
Patients with grade toxicities 4	No	
	Yes	
	Total	
Patients with grade 5 toxicities	No	
	Total	
No. of gradetoxicities≥3per patient ¹	None	
	1 toxicity	
	2 toxicities	
	3 toxicities	
	4 toxicities	
	Total	

1: Patients could present more than one toxicity of the same grade

Table 42. Time between initiation of treatment and toxicity (days)

	Mean (SD)	Median (Min-Max)
Time between initiation of treatment and toxicity (days)		

The frequencies of toxicities with grade ≥3 are shown below.

Table 43. Toxicities with grade ≥3

Type of Toxicity	Grade 3 N (% ¹)	Grade 4 N (% ¹)

1:% calculated with respect to the total number of patients evaluable for safety (n = XX)

Below is a list of the toxicities with grade \geq 3 per patient with their characteristics.

Table 44. List of grade \geq 3 toxicities (patients may present more than one toxicity)

Patient code	Toxicity and Grade	SAE	Relationship with treatment	Start	date AE End date AE

The most frequent toxicities with their degrees and in ANNEX I : LIST OF TOXICITIES A list of all toxicities is presented.

Table 45. Most frequent toxicities (> 10% on = 5) and their grade

		N (%)
XXXX	Absence	
	Presence	
XXXX	Absence	
	Presence	

Table 46. Median time between initiation of treatment and toxicity in the most frequent toxicities (days)

Time between initiation of treatment and toxicity	
Type of toxicity (most frequent)	Median (days)

Table 47. Median time between the start of treatment and toxicity in the most frequent toxicities (days) as a function of the MRG rate

Type of Toxicity		Rate of best global response TMRG (PR or CR) (modified WHO criteria)	Median (days)
Adverse Event	XXXX	No	
		Yes	
		Total	
	XXXX	No	
		Yes	
		Not evaluated	
		Total	

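### SAP Table 47 compares uncensored median time to toxicity by confirmed response, which tends to put responders later even when response and toxicity are unrelated

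*SAP*

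**What the plan says.** SAP 1.6, run on the treated population, lists Table 47 as "Median time between the start of treatment and toxicity in the most frequent toxicities (days) as a function of the MRG rate". The grouping column is "Rate of best global response TMRG (PR or CR) (modified WHO criteria"; its rows are No and Yes, with *Not evaluated* in one of the two blocks only. The single result column is a median in days. The shell has no N, censoring rule, landmark or test, and no definition of *Not evaluated*.

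The protocol fixes when response can be known. Section 6.4.2 schedules tumour assessment "at weeks 12 and 16-18 and then, every 8-10 weeks". Section 6.4.2.g counts a CR or PR only if a second evaluation confirms it, "performed no less than 4 weeks after the criteria for response are first met".

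Dosing and AE collection are as follows:
- Section 5.1.1: "Each patient will receive ipilimumab 3 mg/Kg every 3 weeks, for a total of 4 administration".
- Section 8.3.3, nonserious AEs: "In general, the collection period will last for 30 days after the last treatment administration". It then widens this for one class: "The exceptions are the immune-related AEs that occur within 90 days of discontinuation of dosing of the investigational product".
- Section 8.3.1 collects serious AEs for 90 days after dosing stops.
- Section 9.4.3 sets the safety reporting period "from the first dose of study medication to 90 days (> 5 half lives) after the last dose is received".
- Section 6.3.2 instead reports AEs up to and including follow-up visits, and Table 12 shows AE collection throughout the study.

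The SAP does not say which of these windows feeds Table 47.

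**The concern.** The table groups patients by something that happens after baseline and that requires survival. A confirmed responder is guaranteed a long observation period. The non-responder group can include patients who died within weeks, or who stopped after one to three doses and whose AE collection closed sooner. In that group, toxicities that would have started late are cut off, while early ones are kept. A raw median over observed events is then pulled down among non-responders and hardly at all among responders.

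This is the SAP's only toxicity-by-response comparison. In an immunotherapy trial readers look for a link between immune toxicity and benefit, so a gap caused by unequal observation could be read as biology.

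**Working it through.** The documents give no figure for Table 47, so there is nothing to reproduce. The check asks how large a gap appears when onset has the same distribution in both groups.

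**Inputs from the documents.** First dose is day 0 and planned doses fall on days 0, 21, 42 and 63. The first scheduled scan is at week 12, 12 × 7 = day 84. Confirmation comes at least 28 days later, 84 + 28 = day 112, about week 16. AE windows are last dose + 30 or + 90 days; after four doses that is day 63 + 30 = 93 or 63 + 90 = 153. One-year survival is 20% under the historical assumption and 35% under the target (Protocol 9.1). Protocol 1.3.4 says immune-related AEs commonly start within 3 to 10 weeks.

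**Deaths before response can be confirmed.** With exponential survival, P(death before day t) = 1 − S^(t/365), where S is one-year survival.
- S = 0.20: 1 − 0.20^(84/365) = 31% before day 84; 1 − 0.20^(112/365) = 39% before day 112.
- S = 0.35: 21% and 28%.

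On the scan schedule none of these patients can be a confirmed responder.

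**Size under no association.** Simulation, 2,000,000 patients per setting. Assumptions: exponential death; a 10% response rate, with responders drawn from those alive at day 112 and given all doses while alive; non-responders stop with probability 0 or 12% before each later dose; AE window = the earlier of death and last dose + 30 or + 90 days; lognormal onset with log-SD 0.7; constant hazard with mean 150 days. The range covers both survival rates, both stopping rates and both windows.

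| Onset (same in both groups) | Responder minus non-responder median, days: early deaths counted as No | Deaths before day 84 removed from No |
|---|---|---|
| Days 1–14 | about 0 | about 0 |
| Uniform, weeks 3–10 | 1 to 3 | 0 to 2 |
| Lognormal, median 45 days | 2 to 5 | 0 to 3 |
| Lognormal, median 75 days | 2 to 8 | 0 to 4 |
| Constant hazard | 3 to 14 | 0 to 6 |

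Two worked cases, both with 20% survival, 12% stopping and the 90-day window:
- Lognormal, median 45: 43.3 days in responders; the gap is 4.4, so 43.3 − 4.4 = 38.9 in non-responders.
- Constant hazard: 56.9 days in responders; the gap is 13.5, so 56.9 − 13.5 = 43.4 in non-responders. Lengthening the mean to 200 days gives a gap of about 14.4 days, hence an upper figure of about 15.

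If AEs are collected until death, as Protocol 6.3.2 and Table 12 might imply, the lognormal and uniform gaps stay within 1 to 8 days and the constant-hazard gap is about 12 to 18. The tendency does not depend on the fixed post-dose window.

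**Noise.** In simulated trials of 56 patients (10% responders, 25% with the toxicity, 20% one-year survival), the responder median was later in 54–60% of trials in which both groups had events; chance is 50%. The 3 mg/kg response rates in the protocol, 4.2% (Table 10) and 10.9% (section 1.3.5.b), give 0.042 × 56 = 2.4 and 0.109 × 56 = 6.1 responders, and fewer still with any one toxicity.

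**The case against.** The other side has several good points.

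- A non-responder who lives through four doses has the same AE window as a responder, and the protocol's study design section recommends all four doses despite apparent progression if performance status is stable. The gap comes only from early death or early stopping. This stands.
- Patients who die before the week-12 scan may go to *Not evaluated*, which removes most of the death-driven part. This stands as a possibility, but the row is undefined and appears in one block only. Protocol 9.3.2.2 keeps all treated patients in the response denominator, which points the other way. Up to about 6 days remain with early stopping.
- Large gaps need a constant hazard, which fits poorly with onset in weeks 3 to 10. This stands; a few days is the realistic size for such events.
- Table 14 of the protocol allows a confirmed response before week 12, so survival to week 16 is required only for responses found at scheduled scans. This stands.
- Sampling noise dominates and the table is descriptive. Both are true, and both lower the priority. Neither makes the comparison valid, and without N the reader cannot see that a median may rest on one or two patients.

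**Conclusion.** The point holds in a limited form. Table 47 compares uncensored medians between groups with unequal observation, and the expected direction is later toxicity in responders. The size is near zero for onset in the first two weeks, roughly 1 to 5 days around weeks 3 to 10, and up to about 15 days under a constant hazard with the 30- or 90-day window. These figures rest on exponential survival at the protocol's 20% and 35% and on the assumed response rate, stopping rates and onset shapes.

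A reader might infer more: that responders must show later toxicity by construction, or that late toxicities can be seen only in responders. The documents do not support either, because non-responders who complete treatment are observed equally long and a single trial of this size could show either order. Nor do Tables 42 and 46 share the bias: they have no response split. They are onset summaries among patients with the event and can stay with N shown. Priority is minor. No protocol objective or decision rule uses the table, and the primary endpoint is unaffected.

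**What to change.** Replace Table 47 with a week-12 landmark table. Among patients alive and assessed at week 12, cross-tabulate confirmed CR/PR (yes/no) against onset of the given toxicity before week 12 (yes/no). Then:
- show N in every cell, and the number excluded by death before week 12;
- state the AE window, after reconciling Protocol 6.3.2 and Table 12 with sections 8.3.1, 8.3.3 and 9.4.3;
- define *Not evaluated*;
- label the table exploratory, and add N to Tables 42 and 46.

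The window matters for the landmark itself. With 90 days, even a patient given one dose is covered to day 90, past day 84. With 30 days, a patient stopping after the third dose is covered only to 42 + 30 = day 72, so the number with fewer than four doses should be shown for events collected that way.

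The cost is SAP wording and one re-specified table, using dates already collected. Early deaths and toxicities after week 12 leave the response comparison, and onset time by response is no longer shown.

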1.7. AEs

As specified in the protocol for this analysis, was used the population of treated patients, n = XX.

Table 48. AEs

		N (% ¹ 95% CI)
Patients with at the least one AE, any grade	No	
	Yes	
	Total	
Patients with at the least one AE grade≥3	No	
	Yes	
	Total	
Patients with AEs grade 3	No	
	Yes	
	Total	
Patients with AEs grade 4	No	
	Yes	
	Total	
Patients with Grade 5 AEs	No	
	Total	
No. of Grade AEs ≥3 per patient ¹	None	
	1 AE	
	2 AEs	
	3 AEs	
	4 AEs	
	5 AEs	
	11 AEs	
	Total	

1: Patients could present more than one AE of the same grade

. present the frequencies of AEs with grade ≥3.

Table 49. with grade ≥3

AEType of AE	Grade 3 N (% ¹)	Grade 4 N (% ¹)

1: % calculated with respect to the total number of patients evaluable for safety (n = XX)

Table 50. Time between start of treatment and AE

	Mean (SD)	Median (Min-Max)
Time between initiation of treatment and AE		

Below are the most frequent AEs with their grades and in ANNEX II: LIST OF ALL AEsAEs a list of allis presented.

Table 51. AEs most frequent (> 10% or= 5) and its grade

		nN (%)
XXXX	Absence	49 (84.5%)
	Presence	9 (15.5%)
XXXX	Absence	43 (74.1%)
	Presence	15 (25.9%)

1.8. SAE

ALL / Related

As specified in the protocol, was used for this analysis the treated patient population, n = XX.

Table 52. SAEs

		N (% ¹ ; 95% CI)
At least one SAE	No	
	Yes	
	Total	

1:% with respect to **included patients** with available data.

The SAEs with their details are presented below:

Table 53. List of SAEs with details

Relationship with AE No. treatment	Patient code	SAE and grade	Specify relationship AE	Start date AE	End date AE
No	1				
	2				
	3				
Yes	1				
	2				
	3				

The following are the frequencies of SAEs not related to grade ≥3.

Table 54. Unrelated SAEs with grade ≥3

Type of unrelated SAE	Grade 3 N (% ¹)	Grade 4 N (% ¹)

1:% with respect to ***included patients*** with available data.

Below are the frequencies of unrelated SAEs of any grade.

Table 55. List of unrelated SAEsunrelated

Type ofSAE	N (% ¹)

1:% with respect to ***included patients*** with available data.

1.9. DEATHS

***As specified in the protocol for this analysis, the treated patient population, n = XX, was used.
Deaths in the study or within 30 days after the last dose: ALL / drug related***

Table 56. Deaths during the study

		N (% ¹ ; 95% CI)
Deaths during the study or within 30 days after the last dose	No (Exitus but considered out of study)	
	Yes	
	Not applicable (no death)	
	Total	

1:% regarding the *patients included* with available data.

Table 57.list

Exitus during the study or in the 30 days after the last dose	No.	Patient code	Exitus reason	Exitus reason other	Date of last ipilimumab cycle	Date Exitus	OS time (months since 1st ipilimumab cycle)
No (exitus considered out of study)	1						
	2						
	3						
Yes	1						
	2						
	3						

